An abbreviated 15-item profile of mood states (POMS) questionnaire will be adapted to Spanish based on norms and factor structure reported in Hispanic/Latino populations (74) at the conclusion of each trauma session to assess levels of distress. Subjects will also complete a battery of self-report measures of PTSD symptom severity, subject Unit of Distress ,(impact of events scale—revised, IES-R (75), anxiety (the Spielberger State and Trait Anxiety Scales and Anxiety Sensitivity Index (ASI) (76), depression (Beck Depression Inventory, (BDI-II) (77), alexithymia (Toronto Alexithymia Scale-20, TAS-20 (78), multidimensional interoceptive awareness Scale, and dissociation using the Dissociative Experiences Scale -2 (DES-II) (79), early trauma (Early Trauma Inventory, (ETI) (80), Perceived Support Network Inventory, and Brief COPE. Surveys that have been translated and are archived by CLaRO will also be included, such as measures of psychological symptomatology (Brief Symptoms Inventory (BSI) (81) depression (The Center for Epidemiological Studies Depression Scale (CESD) (82) anxiety (General Anxiety Disorder Scale (GAD-7) (83)) and intimate partner violence (HITS Tool for Intimate Partner Violence Screening (HITS) (84). The Physical Symptoms Questionnaire (PHQ-15), Pittsburgh Sleep Quality Index (PSQI) and Patient Health Questionnaire (PHQ) will also be administered. To assess HIV-associated neurocognitive dysfunction a neurocognitive battery will be administered and performance compared with published age- and education-adjusted normative data to calculate z scores (NPZ), within several cognitive domains. These domains include global functioning (Trail Making Test (TMT), Hopkins Verbal Learning Task, Brief Visual Memory Test, WAIS-R Digit symbol substitution, WAIS-R Digit Span, WAIS-R letter number sequencing, WAIS-R Design Block Test, COWAT (Spanish), Paced Auditory Serial Addition Test, Rey Complex Figure Test, Verbal Fluency Task, Stroop Color-Word Interference Test, Grooved Pegboard, and Iowa Gambling Task. Anti-retroviral regimen will be assessed with the Adult (ACTG) structured interview (69). Health Markers for Review of Systems, Basic Demographic Questionnaire, Pittsburgh Sleep Quality Index, and Physical Health Questionnaire. Individuals randomized to the S-WED group will be prompted to self-report in Spanish i.e., (anger or “enojo”, anxiety or “ansiedad” and depression or “tristeza”. Note: “arrepentido por cosas hechas”= regret about things done, desanimado= unmotivated, inútil= helpless, aterrorizado= terrorized, and culpable= guilty”. Pronoun use will also be quantified from their responses, as research suggests that trauma victims that use more first person singular pronouns (e.g. I/mine, “yo/mio”) in trauma narratives have worse, long-term symptom severity(86)), which extend to broader use of singular pronoun use (87). A similar pattern was observed in depressed and negative mood individuals (84).

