Each encoding block is followed by a distracter epoch (19.5 s), where participants attend to a series of letters (i.e., “XXXXX—YYYYY”) to mimic the active stimulus. This is included to discourage rehearsal. Participants pressed with their right index finger when they saw the letters to control for motor activity in the other conditions. Immediately after each distracter epoch was a 19.5 s recall epoch, during which participants saw the first word of each pair from the encoding epoch that preceded it (e.g., UP - ___), attempted to recall the second word silently (3 s), and viewed a black screen (0.9 s). Subjects indicate perceived success at recalling the second word with a right index finger response and perceived failure with a left index finger response. After each recall epoch, participants focused on a crosshair (6 s) to allow for brain activity to return to its baseline. The sequence of encoding epoch, distractor epoch, and recall epoch repeated ten times. Before each new epoch began, there was a 3 s prompt to inform the participant which task they would need to perform. The full presentation of the task will last 12 m and 24 s.

The following neuropsychological tests and surveys will be administered during session 1 and 2. All forms are submitted and approved by IRB. Each assessment takes between 5 and 15 minutes to complete.

IRB Study Number: 20190760

Version: 10 Date: 06/06/2022

Table 1. Schedule of Assessments

Domain	Measure	T0 screen	T1 pre	T2 write	T3 write	T4 write	T5 write	T6 post
Cognitive	Mini-mental State Exam screener		X					
Psychiatric	Mini-International Neuropsychiatric Interview		X					
	Treatment Outcome PTSD Scale (TOP-8)		X					X
	PTSD Checklist for DSM-5 (PCL-5)		X					
	Civilian Spanish-English version PCL-C		X					
Acculturation	Brief Acculturation Scale For Hispanics (BASH)		X					
	Bidimensional Acculturation Scale (BAS)		X					
Psychosocial	Subjective Unit of Distress		X	X	X	X	X	X
	Impact of events scale—revised		X					X
	Spielberger State-Trait Anxiety Scales		X					X
	Anxiety Sensitivity Index		X					X
	Beck Depression Inventory		X					X
	Toronto Alexithymia Scale		X					X
	Multidimensional Interoceptive Awareness Scale		X					X
	Dissociative Experiences Scale		X					X
	Early Trauma Inventory		X					X
	Perceived Support Network Inventory		X					X
	Brief COPE		X					X
	*Brief Symptoms Inventory		X					X

IRB Study Number: 20190760

Version: 10 Date: 06/06/2022

	*Center Epi- Studies Depression Scale		X					X

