	*Self/other- compassion scales		X					X
	External and Internal Shame Scale (EISS)		X					X
	*HITS Intimate Partner Violence Screening Tool		X					X
	Religion & Spirituality Questionnaire		X					X
	Profile of Mood States		X	X	X	X	X	X
Neurocognitive	Trail Making Test		X					X
	Hopkins Verbal Learning Task		X					X
	Brief Visual Memory Test		X					X
	WAIS-R Digit Symbol Substitution		X					X
	WAIS-R Digit Span		X					X
	WAIS-R Letter Number Sequencing		X					X
	WAIS-R Block Design Test		X					X
	COWAT		X					X
			X					X
	Paced Auditory Serial Addition Test		X					X
	Rey Complex Figure Test		X					X
	Verbal Fluency Task		X					X
	Color-Word Interference test		X					X
	Grooved Pegboard		X					X
	Iowa Gambling Task		X					X
Behavioral	Adult (ACTG) structured interview		X					X
	Self-compassion task		X					X
Biomarker	Saliva for CORT or ACTH & sAA via ELISA		X					X
	Serum and plasma for NFkB & FBPK5		X					X
	Serum and plasma aliquots for storage		X					X

IRB Study Number: 20190760

Version: 10 Date: 06/06/2022

Health Markers							
	Review of systems		X				X
	Basic Demographic Questionnaire		X				X
	Pittsburgh Sleep Quality Index		X				X
	Physical Health Questionnaire		X				X

11) Specimen Banking*

Participants will be asked to abstain from illicit recreational substances, caffeinated and decaffeinated substances, aspirin and other medications, alcohol and strenuous exercise, and to fast from 10 pm on the night before arrival to the Behavioral Medical Research Center (BMRC) between 8 and 10 am before each visit. Participants will be advised to consult their physician before beginning the fast if the schedule varies from normal eating patterns. On the first visit, a urine toxicology screen (i.e., alcohol, barbiturates, benzodiazepines, LSD, PCP, THC, morphine, and amphetamines) will be performed. Urine samples will not be stored after analysis.

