13) Data Storage

MRI scans obtained at the UM Cox Annex MRI facility will be de-identified and housed at the University of Miami in a secure data server for large imaging files. The Department of Psychology at the University of Miami also maintains a secure server where de-identified data can be stored under a subject ID. Access to this server is password protected and data is encrypted. Data will be uploaded to the secure server, whereby only the PI will have direct access. After uploading data to the secure server hard-copies of forms with all subject data is kept under lock and key in a secured cabinet, inside a limited access door (NIS Room 101-C) and will only be available to study personnel. All data will be de-identified and stored, used and transmitted entirely separate from other participant data. Informed consent forms will be kept under lock and key in room 1520 of the CRB with card access available into the room by PI only.

Study Research Coordinator will be responsible for ensuring quality control of all data. Specimen data collected from the second blood draw at time point 2 will be processed and plated on the third floor of the NIS building. After preparing the sample for endothelial cell assay using flow cytometry, the sample will be frozen and stored on the third floor of the NIS building and then later transferred in a secured medical courier container, to the 7th floor of the BMRC. Flow cytometry will be conducted in conjunction with the Flow Cytometry Core of the Diabetes Research Institute, under the direction of [name]. The Research Coordinator will have received and provided proof of updated training in the responsible conduct of research.

14) Provisions to Monitor the Data to Ensure the Safety of Subjects*

Based upon the querying of traumatic events, participants will be closely monitored for suicidal ideation (SI). Upon endorsement of survey items indicative of SI or

IRB Study Number: 20190760

Version: 10 Date: 06/06/2022

reporting SI during interview or trauma recall the following steps will take place in conjunction with the suicide risk packet.

- (1) Participant discloses suicidal ideation verbally or through administration of a study instrument.
- (2) Assess the risk and severity of suicidal ideation using the HPAC Suicide Assessment (see measures).

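### Close monitoring for suicidal ideation is promised, but the public text schedules no question about it at the four writing sessions

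*Combined protocol and SAP*

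**What the plan says.** Section 14 opens with the promise "Based upon the querying of traumatic events, participants will be closely monitored for suicidal ideation (SI". No instrument, visit or frequency is attached to it. The response pathway begins "Upon endorsement of survey items indicative of SI", or when SI is reported in an interview or during trauma recall. The HPAC Suicide Assessment is used only after that.

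The adverse event text in Section 14 says that part of the psychosocial battery covers SI and names two sources: the MINI, reviewed as screening data, and a single item of the Beck inventory. In Table 1 the row "Mini-International Neuropsychiatric Interview" is marked at T1 only, and the row "Beck Depression Inventory" at T1 and T6 only.

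At the writing sessions, T2 to T5, the rows marked in the psychiatric and psychosocial blocks are "Subjective Unit of Distress" and "Profile of Mood States". Section 10 describes the second as "An abbreviated 15-item profile of mood states (POMS) questionnaire", used "at the conclusion of each trauma session to assess levels of distress". Section 15 adds a question on how upset the participant is about the day's topic. When distress is raised, Section 14 provides for coping and stress-management advice from a distress packet.

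Sections 15 and 16 add human contact: a check-in of about 2 minutes by a bilingual trauma therapist with every participant, debriefing after trauma recall, supervision by a trained therapist, a coordinator contact at 24-72 hours after writing, and weekly contact with staff.

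**The concern.** Section 17 rates the study as more than minimal risk because severe trauma is recalled, and Section 15 excludes women with recent or current SI for safety. Entry requires elevated PTSD symptoms (Section 6). Women in two of the three arms then write repeatedly about the worst experience of their lives, and one probe asks how it affects their self-worth (Section 8).

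If close monitoring for SI is meant anywhere, one would expect it during these weeks. In the public schedule, the instruments that ask about SI fall before the writing starts and one month after it ends (Section 9). The instruments used in between measure distress. SI that begins during the intervention could therefore go unasked about at the sessions themselves, and a high distress score has no stated link to the suicide assessment.

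**Working it through.** The plan gives no figure to reproduce. The check sets the promise beside the schedule and the safety text.

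**1. What is asked, and when**

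| Element | T1 | T2-T5 | T6 | Described as asking about SI? |
|---|---|---|---|---|
| MINI (Table 1; Section 14) | yes | no | no | yes |
| Beck item (Table 1; Section 14) | yes | no | yes | yes |
| SUDS (Table 1; Section 14) | yes | yes | yes | no, distress |
| POMS (Table 1; Sections 10, 14) | yes | yes | yes | no, distress |
| How-upset question (Section 15) | no row | before and after writing | no row | no |
| HPAC (Section 14) | no row | after disclosure | no row | severity assessment, once SI is known |

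**2. Row count for T2 to T5 in Table 1.** Psychosocial: 2 of 18 rows are marked (SUDS and POMS). Psychiatric: 0 of 4. Writing sessions with a stated SI question: 0 of 4. Any other psychosocial survey that contains an SI item is also unmarked at T2 to T5, so the count does not depend on which surveys contain one.

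**3. Two features of the table that could mislead.** The health-marker rows have one column fewer after the page break, so their second mark could be misread as T5. This looks like an artefact of text extraction, and none of those rows is described as an SI measure. The sentence that introduces Table 1 speaks of sessions 1 and 2, while the table marks T1 and T6. I read that sentence as meaning the two assessment visits.

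**4. Contacts outside the table.** The therapist check-in gives particular attention to women whose scores show distress. The 24-72 hour contact has elevated distress as its stated purpose. The weekly contact concerns problems that might warrant withdrawal. Debriefing offers support and information. None is stated to include an SI question.

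**5. What starts the HPAC steps.** There are two triggers: verbal disclosure, and endorsement on an instrument. The first operates at every contact. The second has no stated SI instrument to act on at T2 to T5. No text links a raised SUDS or POMS score to HPAC.

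**6. Size of the change.** Added items: 4 sessions x 1 item = 4 per woman; 4 x 36 = 144 at full attendance.

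**7. Expected yield.** Section 15 reports that fewer than 5% needed extra counseling in earlier writing trials: 0.05 x 36 = 1.8, so fewer than 2 of 36 women. This is a counseling rate, not an SI rate, and indicates only the order of magnitude.

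**The case against.** The strongest reply is that absence from Table 1 proves little. The table omits the how-upset question, the HPAC assessment and the PC-PTSD-5 used at screening, so it is not a full list of what participants are asked. The suicide risk packet, the distress packet and the content of the check-in are cited but not public, and any of them may already ask about SI. The promise names no instrument, and a trauma therapist speaking to every woman is a coherent way to monitor. The documents offer no evidence that one self-report item would detect more.

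Much of this stands. The finding is that the public text states no SI question at T2 to T5, not that none is asked. The reply does not remove the mismatch: the promise is specific to SI, while every stated purpose and measure at the writing sessions concerns distress.

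Three stronger readings are tempting, and the documents do not support them.

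- A reader might infer that SI arising in the writing weeks would surface only if the woman volunteered it. That underweights the therapist check-in, the debriefing and the therapist supervision. Essays also reach staff after each session (Section 9), though no review time is given.
- A reader might express the gap as a share of the days between SI questions. The previous ones are at T1, and the interval from T1 to the first writing session is not stated, so the share cannot be calculated.
- A reader might add that the Beck item lacks a same-visit review at T1 and T6. Endorsement already starts the HPAC steps and an exit interview follows the surveys (Section 8), so this is at most a wording point.

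**Conclusion.** The point holds in limited form, and I would label it a cheap improvement. The public text promises close monitoring for SI and schedules no SI question at any of the 4 writing sessions. It also states no step from raised distress to the suicide assessment. It would be wrong to conclude that participants are unmonitored there: several safeguards are planned, and verbal disclosure starts the HPAC steps.

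The conclusion rests on two assumptions: that Table 1 and Sections 14 to 16 reflect what is done at the sessions, and that the unseen packets and check-in add no SI question. If the second is wrong, what remains is a documentation gap. The expected yield is small, since recent or current SI, current treatment of major depression and self-reported psychiatric disorder are all grounds for exclusion. That lowers the risk without removing it.

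**What to change.** 1. In Table 1, add the single Beck SI item, already used in the study, at T2, T3, T4 and T5 in all three arms.
2. In Section 15, have the designated therapist read the answer at the existing safety check, before the session closes.
3. In Section 14, state that any positive answer starts the HPAC steps, whatever the SUDS or POMS score.

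If the check-in or the packets already ask about SI at these sessions, saying so in Table 1 and Section 15 is enough for the first step.

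**Cost.** One amendment and 144 short answers in total, with no new instrument or staff role. The main burden is operational. Section 9 describes the writing as online, so the therapist must be reachable, and the participant's location and phone number known, before each session closes. Section 7 mentions a private office; if sessions are held in person, the burden is smaller. The change does not cover the month between the end of writing and T6.

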- (3) Based on the suicide assessment outcome and consultation with the postdoctoral fellow and/or supervisor, determine whether the participant is at low, moderate, severe, or extreme risk of suicide.
- (4) Decide on next steps depending on risk level (in consultation with postdoctoral clinical fellow, who will then consult with primary or backup supervisor as indicated in the Suicide Risk Assessment Packet).

Participants will also be monitored for elevated levels of psychological distress throughout the course of the study. Specifically, participants will be queried regarding their distress levels before and after each session using the SUDS as well as the POMS. These measures will be scored immediately following each session. If levels of distress are elevated, we will go over ways of reducing distress via coping and stress management strategies in conjunction with the distress packet:

- (1) Things I can do to help cope (e.g., exercise, playing music, relaxation exercises, hot shower, journaling, etc.).
- (2) People I can contact to distract and/or support me (e.g., friend, therapist, mentor, relative, religious leader, etc.)
- (3) Three positive things I can focus on right now (e.g., something good in my life, something positive that happened, a beautiful sunset, people who care about me, an inspirational thought, a nice memory, etc.).

Access to participant records will be limited to the study staff. All records are kept using a study ID number. Participant number and name will appear together only on one form. That form will be kept in a separate locked cabinet to which only the lead Study Coordinator will have access. All other forms will contain only study ID number. Participant name or other identifiable information will not appear when we present this study or publish its results. Any staff with access to identifying information will be required to sign a confidentiality pledge, which prevents them from sharing any personal information with anyone else. The signed informed/consent form will stay with PI. Only coded information will be shared with researchers and other doctors that are part of this study.

Participants will be informed that they have the right to have their data (specimen, neuroimaging, psychometric) destroyed at any time following completion of the study.

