All MRIs will be reviewed by a neuroradiologist in the Division of Radiology at the Miller School of Medicine. The research team would provide de-identified images of the MRI scan and limited information (age and gender) to help the radiologist examine the images. The radiologist would generate an MRI Summary Report for

IRB Study Number: 20190760

Version: 10 Date: 06/06/2022

each MRI that is performed. The principal investigator would communicate any results of clinical significance to the research participant. A copy of the written report will be provided to allow the participant to communicate with his/her medical doctor. The participant may also request a copy of the scans. After obtaining written permission, a copy of scans will be given to the participant.

A plan for ensuring safety of the participant will be establishing a data monitoring committee and a plan for reporting findings to the IRB. The data monitoring committee will consist of two components. Progress and issues associated with the collection of specimens will be reported to [name] M.D. Ph.D., Director of the Comprehensive AIDS Program, Clinical Director of the Adult HIV Section for Infectious Diseases and Professor of Medicine at the University of Miami Miller School of Medicine. Periodically, the PI will evaluate data collected in order to make sure participant data remains safely acquired and stored. This will include review of a daily log of all interactions with participant that will be provided by the Study Coordinator. Once per week an existing subject ID will be selected at random by the PI. The research coordinator will then need to provide a report on the location and secured state of the data collected, including but not limited to assessment forms, specimen sample & assay banks, encrypted data on server, along with any logs collected via direct or indirect communication with the participant

Adverse Event

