In the event of any untoward events or conditions that endanger the participant's health, safety, and rights, suspension of the research will occur barring a full report of the event to the University of Miami IRB. In the case of an adverse event, i.e., unanticipated problem associated with the study, a report will be made indicating: 1) type related to psychological/mental or physical events; 2) severity related to the degree to which psychiatric or medical intervention is required; 3) scope of the event related to the impact it had on the participant's ability to complete all study requirements; 4) consequence of the overall event; and 5) if applicable, frequency of the problem. This report will be forwarded to the HRSO office within 10 days of the study team becoming aware of the adverse event. A section of our psychosocial surveys do address suicidal ideation. In order to minimize risk to the participant we have added language to the confidentiality section regarding our intention to intervene if suicidal ideation is derived from survey items. Screening data from the MINI psychiatric interview will be reviewed to determine if it meets criteria for moderate to high potential suicide risk, based upon recommended guidelines. In addition, high suicide risk may be assessed by an individual item on the Beck's Depression Inventory-2. The study PI is qualified to complete the evaluation. If the screens are positive and the participant is believed to be at risk, study team members will work with the participant contact their doctor, a trusted family member, or a therapist to discuss their thought. In more critical situations the study staff may work with the individual on a plan that might include getting them safely to a hospital environment. This data will not be reported as a part of the analysis.

IRB Study Number: 20190760

Version: 10 Date: 06/06/2022

15) Provisions to Protect Subjects

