Subject initiated withdrawal from the study may occur at any time during participation in the study. Participants may also refuse to answer survey questions or take part in particular assessments and still be compensated for their time. Participants will be in weekly contact with project staff so that if any issues associated with the intervention warranting withdrawal were to arise, they could be dealt with immediately. Also, upon early withdrawal from the study, participants will have the option of having their data immediately destroyed without affecting compensation for their time.

17) Risks to Subjects*

The research does pose greater than minimal risk to subjects due to recall of severe trauma. Participants may feel uncomfortable about some of the questions that they are being asked. They may choose not to answer any question that they do not want to answer. Subjects may become frustrated when performing tasks. During the consent process, subjects will be told that they should do their best. The procedures may be long and boring. These procedures will be completed with interspersed breaks to reduce any fatigue or discomfort.

IRB Study Number: 20190760

Version: 10 Date: 06/06/2022

As a part of the phlebotomy protocol participant's heart rate and blood pressure will be taken prior to blood draw. If elevated blood pressure indicative of Stage 2 hypertension (160/100), any heart rhythm problems or evidence of underlying heart disease are found, we will inform the subject promptly, stop the test and refer the participant to see a cardiologist.

Bruising, bleeding, and rarely infection could occur at the site where the needle enters the vein. To reduce these risks, blood samples are taken in a sterile manner and lines will be routinely checked during the experiment by an experienced phlebotomist and registered nurse. Uncommonly, fainting might occur.

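### Conflicting adverse-event triggers and the exclusion of suicide-risk data leave the expected, non-endangering harms of trauma writing without a planned count by arm

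*Combined protocol and SAP*

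**What the plan says.** Section 14, under Adverse Event, opens with a trigger based on danger: "In the event of any untoward events or conditions that endanger the participant's health, safety, and rights, suspension of the research will occur", together with a full report to the IRB. The next sentence sets a trigger based on expectation: "In the case of an adverse event, i.e., unanticipated problem associated with the study, a report will be made indicating" type, severity, scope, consequence and, if applicable, frequency. This second report goes to the HRSO office within 10 days. Its first item is "type related to psychological/mental or physical events", so psychological events are within its scope. Study arm is not among the five items.

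The same text describes the suicide-risk screen (the MINI interview and one BDI-II item) and the response to a positive screen. It ends: "This data will not be reported as a part of the analysis".

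The plan expects these harms. Section 14 monitors suicidal ideation and has staff "determine whether the participant is at low, moderate, severe, or extreme risk of suicide". It also measures distress with SUDS and POMS before and after each session. Section 15 anticipates that a few women will need extra counselling time and includes a distress management plan with referral and an offer to withdraw. Section 17 rates the study above minimal risk because of trauma recall.

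The data monitoring committee in section 14 has two components. "Progress and issues associated with the collection of specimens will be reported to" a physician, and the investigator checks that data are safely acquired and stored.

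**The concern.** Trauma writing is meant to bring up distressing material, so its main foreseeable harms are psychological and are foreseen in the plan. A definition that stops at the unanticipated leaves those harms out unless they meet the separate danger test. The two sentences give different answers for the same event, and neither asks for cumulative counts.

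Staff are told what to do for each woman, but no step adds the cases up by randomised arm. The trial could then report benefit from trauma writing in Spanish or English without a planned statement of how many women in each arm endorsed suicidal ideation, were referred for distress, or left because of it. A reader weighing the two trauma-writing arms against daily-event writing would want those counts beside the efficacy result.

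**Working it through.** The plan gives no sample-size, power or error-rate figure for harms, so there is nothing to reproduce. The check is mainly a reading of the text, followed by a small calculation of what counts could show.

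**1. Where each kind of event goes, read literally.**

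| Event after randomisation | Danger trigger (suspension, IRB) | Adverse-event report (HRSO, 10 days) | Planned by-arm count |
|---|---|---|---|
| Suicidal ideation judged to endanger | yes | no, because anticipated | none |
| Suicidal ideation not so judged | no | no, because anticipated | none; BDI-II item excluded |
| Distress needing referral or extra counselling, no danger | no | no, because anticipated | none; SUDS/POMS scores only |
| Withdrawal for distress, no danger | no | no, because anticipated | none |
| Unexpected event, no danger | no | yes | none |

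Rows 2 to 4 are the gap. Rows 1 and 5 show that the two triggers cover different events.

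**2. What the exclusion removes.** Table 1 schedules the MINI at T1 only. Section 9 places randomisation at the second visit, so MINI data cannot show a difference caused by the arms. The Beck inventory is scheduled at T1 and T6. The loss for a by-arm comparison is therefore the T6 BDI-II item, the only suicide-risk item that the plan names and schedules after randomisation. Section 15 excludes women with recent or current suicidal ideation. If that is applied as written, an endorsement at T6 would be new since entry, which makes the item informative.

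**3. What stays in the analysis.** SUDS and POMS are scheduled from T1 to T6 for every participant, and the Impact of Event Scale at T1 and T6. Section 12 (Data Analytical Approach) covers all psychometric and survey data and uses linear mixed models for the effect of intervention exposure. Distress scores can therefore be compared by arm. Section 4 lists no harm outcome, section 14 gives no cut-off for elevated distress, and section 12 names no safety summary.

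**4. What counts could show.** Inputs from section 8: 24 women in the two trauma-writing arms and 12 in control, 24 + 12 = 36. An equal split of the 24 (12 and 12) is assumed.

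- Exact two-sided 95% upper limit with zero events in n women: 1 − 0.025^(1/n). For n = 12: 1 − 0.025^(1/12) = 26.5%. For n = 24: 14.2%. For n = 36: 9.7%.
- Fisher's exact test, two-sided, against 0/12 in control: 4/12 gives p = 0.093 and 5/12 gives p = 0.037. For the pooled trauma-writing arms, 7/24 gives p = 0.070 and 8/24 gives p = 0.033.

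A formal test would miss all but very large differences. Counts with exact intervals are the appropriate summary.

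**The case against.** The other side has a strong case, and most of it limits the point.

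- A reader might infer that distress is never compared between arms. The documents do not support that. SUDS and POMS are collected throughout in every arm and fall under the section 12 analysis statement, and worsening of PTSD symptoms would show on a primary outcome. What stands is that mean scores do not count endorsements, referrals or withdrawals, and that these scales are not designated as safety outcomes.
- A reader might infer that anticipated harms reach no oversight body. The danger trigger is not limited to unanticipated events, so a dangerous but expected event still goes to the IRB. That is a report on an event, not a cumulative summary by arm.
- A reader might infer selective loss of the worst-affected women, because "upon early withdrawal from the study, participants will have the option of having their data immediately destroyed". Nothing in the documents shows that distressed women would use this option more than others. It is a participant right, and narrowing it would be an ethics trade-off.
- A reader might turn the section 15 figure of less than 5% into an expected number of adverse events. That figure is past experience of extra counselling time in other trauma-writing trials. It is not a rate set for this trial, and extra counselling is not the same as an adverse event.
- A reader might say the trial cannot support the section 18 statement on benefit and risk. That statement is a prospective justification, not a conclusion the trial sets out to establish.
- Individual care is thorough: a therapist check-in, coordinator contact within 24 to 72 hours of writing, and a daily interaction log reviewed by the investigator. The log could be a source for a count, but section 14 gives its purpose as safe acquisition and storage of data.

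**Conclusion.** The point holds as a gap in reporting. Section 14 contains two triggers that conflict in scope. The narrower one leaves expected, non-endangering harms outside the definition of an adverse event. Suicide-risk data are kept out of the analysis, which would remove the T6 BDI-II item from any by-arm report. Neither stated component of the committee reviews harms.

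No error rate, estimate or sample size is affected. What is missing is descriptive: three or four rows of counts for arms of about 12 women, where even zero events would be compatible with a true rate of up to 26.5%.

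The conclusion rests on two readings. The first takes the equation of adverse event with unanticipated problem literally. The second takes the excluded data to be the MINI and BDI-II suicide-risk information just described; the reach of that sentence is not stated, and a wider reading would exclude more. This should be corrected, but it does not threaten the primary analysis.

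**What to change.** 1. **Section 14, Adverse Event.** Reconcile the two sentences. Define an adverse event as any untoward psychological or physical occurrence, anticipated or not, and keep the unanticipated problem as the subset that triggers the 10-day report. Which events lead to suspension is for the sponsor and the IRB to settle; the text should give one answer.
2. **Section 14, suicide-risk sentence.** Replace it with a commitment to de-identified descriptive counts by arm, with exact intervals and no formal test, of post-randomisation suicidal-ideation endorsement (including the T6 BDI-II item), distress referrals, and withdrawals for distress.
3. **Oversight.** Send the cumulative table to the physician already on the committee and to the mental-health supervisor in section 15.
4. **Section 16.** Leave the participant's data-destruction option unchanged.

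The cost is an amendment, one log and one small table, drawn largely from information already collected. The limitation is that the counts will be too small for testing at 12 per arm, and the report should say so.
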